8.2 Adverse events

8.2.1 Data considerations

Adverse events will be recorded from the time of informed consent until study completion. All AEs will be coded as described in [Section 3.8](#).

In addition, AEs will be classified according to the Common Terminology Criteria for Adverse Events (CTCAE) Version 5 or later for severity. For any AEs where it is not possible to provide a CTCAE grading, the events will be assessed using a standard intensity classification (mild, moderate and severe). For the purpose of reporting severe AEs, all CTCAE severity classifications will be mapped to a standard intensity classification as described below:

- Grade 1 - Mild

- Grade 2 - Moderate
- Grade 3, 4, 5 - Severe

These will be tabulated together with the AEs that were not classified according to CTCAE criteria (i.e., all Grade 1 AEs as per CTCAE criteria will be included in the ‘mild’ category together with those AEs classified as mild as per the standard intensity classification). In the case a mapped standard intensity classification per above rule is different from the standard intensity classification on CRF, the worst case will be used as the standard intensity classification (i.e. an AE with Grade 1 and moderate as intensity classification will be classified into moderate).

A TEAE is defined as an AE starting on or after the time of first administration of IMP in MG0004 or any unresolved event already present before the first administration of IMP in MG0004 that worsens in intensity following exposure to IMP in MG0004, up to and including 8 weeks (56 days) after the end of the Treatment Period or 8 weeks after the last of IMP in study participants who discontinue the study or IMP.

A persistent AE is defined as an unresolved AE that extends continuously from MG0003 to MG0004 and does not worsen in intensity following exposure to IMP in MG0004. Persistent AEs will be recorded in MG0004 database and as other non-TEAEs will be listed only.

Where dates are missing or partially missing, AEs will be assumed to be treatment-emergent unless evidence exists that does not allow the AE to be treatment-emergent. Handling of missing dates for classification of AEs as TEAEs is described in [Section 4.2.2](#).

The following rules will be used to assign a TEAE to a study period:

- **Treatment Period:** a TEAE will be assigned to the Treatment Period if the start date of the event is on or after the date of the first administration of MG0004 IMP on Day 1, up to 7 days after the last dose of IMP;
- **Observation Period:** a TEAE will be assigned to the Observation Period if the start date of the event is greater than the day after Treatment Period until 8 weeks following the final dose; events starting later than 8 weeks following the final dose of IMP are not considered TEAEs.

A TEAE will be counted as a TEAE related to IMP if the response to the question “Relationship to Study Medication” is “Related”.

AEs will be presented as “number of participants (percentage of participants) [number of events]”. In this style of output, “[number of events]” will include all cases of an AE including repeat occurrences in individual participants, while “number of participants” will count each participant only once.

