8.3.8 Treatment-emergent adverse events

Treatment-emergent AEs are defined as AEs starting after the time of first IMP administration up to and including 8 weeks after the final dose.

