3.6 Treatment assignment and treatment groups

For the analyses using SS by the first dose received, study participants will be grouped according to the dose levels of IMP participants first received [REDACTED] in this study (i.e. before any switching occurs) using the exposure data from CRF. For example, if study participants randomized to IMP [REDACTED] and first received IMP [REDACTED], then these study participants will be allocated to IMP [REDACTED]. If a study participant first received IMP [REDACTED] and then switched to [REDACTED], then the study participant will be allocated to [REDACTED].

For the analyses using SS by the most recent dose received, study participants will be grouped according to the most recent dose level of IMP participants received prior to each visit or the onset of events using the exposure data from CRF. For example, if a study participant first received IMP [REDACTED] and then switched to [REDACTED] prior to Visit 5, then the participant will be allocated to [REDACTED] at Visit 5.

For the efficacy analyses using SS by dose switch during the Treatment Period, study participants will be grouped into dose adjuster or dose non-adjuster. A study participant who receive different dose during the Treatment Period from the randomized dose level will be classified as a dose adjuster, otherwise dose non-adjuster. For example, if a study participant was randomized to and first received IMP [REDACTED] and then switched to [REDACTED], then the study participant will be allocated to dose adjuster.

For the analyses using RS, study participants will be grouped according to the dose levels of IMP to which study participants were randomized.

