- If the stop date is completely unknown, then use discharge date or data cut-off date. Discharge date refers to the date of the end of study visit for completed participants or the date of discontinuation for participants that were withdrawn. For any AEs with known start date after the date of discontinuation, the date of last contact will be used as the discharge date. For participants still ongoing in the study at the time of the data cut-off, and for whom no discharge date is available, the date of the data cut-off will be used instead of the discharge date.

Any medication with a start date on the first dosing date and time unknown, will be assumed to be concomitant.

Imputed AE dates will be used for the calculation of duration of AEs as described in [Table 4-1](#).

Table 4-1: Calculation rules for duration of AEs

Data availability	Onset date	Outcome date	Calculation rules
Complete data	D1	D2	Duration = D2 – D1 + 1 d
Start date partially or completely missing	--	D2	Duration = < D2 – D0 + 1 d Notes: D0 is imputed start date per above rules.
End date partially or completely missing	D1	--	For ongoing AE: Duration = > D3 – D1 d For resolved AE: Duration = < D3 – D1 d Notes: D3 is imputed end date per above rules.

Table 4–1: Calculation rules for duration of AEs

Data availability	Onset date	Outcome date	Calculation rules
Start and end date partially or completely missing	--	--	For ongoing AE: Duration = >D3 – D0 d For resolved AE: Duration = < D3 – D0 d Notes: D0 is imputed start date and D3 is imputed end date per above rules.

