8 SAFETY ANALYSES

All safety analyses will be presented using the SS. Listings will be presented by treatment group and participant; tabulations will be presented by treatment group. Unless otherwise specified, safety analyses will be presented by the most recent dose the study participants received in MG0004 as described in [Section 3.6](#).

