8.2.2 Adverse events summaries

TEAEs will be summarized by the most recent dose level prior to onset of TEAEs and RLZ total, including the number and percentage of study participants and frequency. Additional details are described below:

1. Overview of TEAEs will include following categories: any TEAEs, serious TEAEs, participant discontinuation due to TEAEs, permanent withdrawal of IMP due to TEAEs,

temporary withdrawal of IMP due to TEAEs, TEAEs requiring dose change, treatment-related TEAEs, severe TEAEs, TEAEs leading to death, all deaths (AEs leading to death).

2. Incidence of TEAEs will be summarized by SOC, HLT, PT for:

- Any TEAEs
- Any TEAEs during Treatment Period
- Any TEAEs by maximum intensity (mild, moderate and severe)
- Any TEAEs by relationship
- Severe TEAEs
- Non-serious TEAEs above reporting threshold of 5% of study participants
- Fatal TEAEs
- Fatal TEAEs by relationship
- Serious TEAEs
- Serious TEAEs by relationship
- Participant discontinuation due to TEAEs
- TEAEs leading to permanent withdrawal of IMP
- TEAEs leading to temporary withdrawal of IMP
- TEAEs requiring dose change
- Treatment-emergent AESM
- Treatment-emergent AESI

3. Incidence of any TEAEs will be summarized by decreasing frequency of PT.

AESMs include severe headache, severe GI disorders (i.e., abdominal pain, diarrhea, vomiting), and opportunistic infection.

AESIs are the cases of potential Hy's Law (see [Section 8.3.1](#)).

AESMs and AESIs will be identified based on the assessment by the Investigator as recorded in the CRF. An AE will be counted as an AESM if there is a 'yes' response to the question "Adverse event of Special Monitoring?" and 'no' otherwise. An AE will be counted as an AESI if there is a 'yes' response to the question "Adverse Event of Special Interest?" and 'no' otherwise.

When applicable adverse event summaries will be ordered by alphabetical SOC, alphabetical HLT within SOC and decreasing frequency of PT in the RLZ total column for tables.

Listings of all TEAEs, all non-serious TEAEs, serious TEAEs, permanent withdrawal of IMP due to AEs, study participant discontinuation from study due to AEs, AEs leading to death, AESIs, AESMs will be presented by treatment group and participant. Persistent AEs and TEAE will be flagged in the listings. Most recent dose will be presented in listing even when the AE start date is partial.

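### The SAP assigns TEAEs to study periods by event start date, so a pre-existing event that worsens on MG0004 drug counts as a TEAE but belongs to no period, and its dose column is unclear

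*SAP*

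**What the plan says.** SAP 8.2.1 gives the TEAE definition two limbs. The first is an adverse event starting on or after the first MG0004 dose. The second is "any unresolved event already present before the first administration of IMP in MG0004 that worsens in intensity following exposure to IMP in MG0004". Protocol 9.3.1 has the same two limbs. Protocol 8.3.8 has only the first: "Treatment-emergent AEs are defined as AEs starting after the time of first IMP administration".

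SAP 8.2.1 then places each TEAE in a period. The Treatment Period applies only "if the start date of the event is on or after the date of the first administration of MG0004 IMP on Day 1"; its upper limit is a week beyond the final infusion. The Observation Period applies only "if the start date of the event is greater than the day after Treatment Period until 8 weeks following the final dose".

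For dose columns, SAP 8.2.2 says that "TEAEs will be summarized by the most recent dose level prior to onset of TEAEs and RLZ total". SAP 3.6 describes this grouping as "the most recent dose level of IMP participants received prior to each visit or the onset of events using the exposure data from CRF". The opening of SAP Section 8 ties it to this study: "safety analyses will be presented by the most recent dose the study participants received in MG0004".

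An unresolved lead-in event that does not worsen is a persistent AE under SAP 8.2.1. It is not a TEAE and is listed only. The SAP has no matching placement rule for a carried-over event that does worsen.

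**The concern.** MG0004 is a rollover study. Its Visit 1 is the last lead-in visit, so some participants can be expected to arrive with an unresolved event, and the SAP plans for this with its persistent AE class. An event that gets worse on exposure to the drug is what the second limb exists to catch. If the placement rules cannot handle it, the event is counted as a TEAE and then left out of the tables that describe what happened on treatment.

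The outputs at risk are in SAP 8.2.2 and 8.2.3: the incidence table of TEAEs in the Treatment Period, the headache and gastrointestinal summaries by intensity for that period, and the headache graphs by time of onset relative to infusion. Headache matters most, because Protocol 10.20.1 calls it the most commonly reported adverse drug reaction.

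**Working it through.** No plan figure needs reproducing; the check is whether the rules fit together.

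**Period.** A second-limb TEAE was present before the first MG0004 dose. If it began on an earlier calendar date, its start date fails the Treatment Period rule, which requires the first-dose date or later. It also fails the Observation Period rule, which requires a later date still. Two narrow exceptions exist: an event that began earlier on Day 1 itself, since the rule compares dates, and an event whose missing start date is imputed to the first-dose date under SAP 4.2.2.

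**Dose.** The SAP says onset here, not start date, and does not define onset for a worsened event. Two places suggest that it means start date. In Table 4-1 (SAP 4.2.2) the onset-date column is blank in the row headed "Start date partially or completely missing". SAP 8.2.2 also says that the most recent dose will be listed even if the AE start date is partial. On that reading no MG0004 dose precedes onset. On the other reading, the event becomes a TEAE only when it worsens, so onset is the worsening date and the dose is defined. The text does not settle which applies.

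**Test events.** Assumptions: first dose on day 1, last dose on day 358 (1 + 51 × 7), one change of dose level on day 180, and onset taken as the recorded start date. The Treatment Period then covers days 1 to 365 (358 + 7), and the TEAE window ends on day 414 (358 + 56).

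| Event | TEAE? | Placed by start date | Placed by worsening date |
|---|---|---|---|
| New, day 30 | Yes | Treatment Period, first dose level | not applicable |
| Began day −20, worsens day 30 | Yes | No period, no dose | Treatment Period, first dose level |
| Began day −20, worsens day 200 | Yes | No period, no dose | Treatment Period, second dose level |
| Began day −20, never worsens | No | Listed only | not applicable |

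The missing period follows from the literal text. The missing dose follows only if onset means start date.

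**What remains.** These events are still TEAEs. They stay in the RLZ total column of each applicable TEAE or AEOF table that is not restricted by period, and in the listings. In Treatment Period tables they are lost from RLZ total as well.

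Separately, the Observation Period rule starts after the day following the Treatment Period, so read literally a new event on day 366 (358 + 8) also falls in neither period.

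**The case against.** The strongest reply is that a worsening may be recorded as an AE in its own right. Protocol 10.3.1 lists an increase in the frequency or intensity of a pre-existing condition among events that meet the AE definition. Protocol 8.2.1 has worsened physical findings recorded as AEs. If each worsening gets a new record, its start date falls after the first dose and every rule works. The detailed entry instructions are in eCRF Completion Guidelines that are not part of these documents.

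This stands in part: whether any event is lost in practice depends on that convention. It does not close the gap, because neither document requires a new record or a new date. Protocol 10.3.3 says new or updated information goes in the originally completed eCRF. Under a new-record convention the second limb would also be redundant, since the first would already cover these events.

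Other replies stand and limit the point:

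- A reader might infer that these events are missing from every dose column. The dose rule speaks of onset, which can mean the worsening date, so the text supports ambiguity and no more.
- A reader might infer that they survive only in the RLZ total of the any-TEAE table. They also stay in the serious, severe, by-relationship, withdrawal and AEOF tables that apply and carry no period restriction.
- A reader might expect dose columns that do not add up to RLZ total to reveal the fault. Participant counts need not add up anyway, because someone who switches dose can count in both columns and once in the total. Only event counts would show a shortfall, and only if onset means start date.
- The study is descriptive with no testing (SAP 4.1), so no inference is affected.

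**Conclusion.** The point holds for the period rules. As written, a worsened pre-existing event that began before the first-dose date is a TEAE with no study period, and it is omitted from the Treatment Period outputs named above. For the dose columns the fault is an undefined term. Overall occurrence of TEAEs and of TEAEs leading to permanent withdrawal, the two primary safety endpoints, carries no period restriction and is not reduced.

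The size is unknown, because neither document gives the number of carried-over events or how often they worsen. Purely as an illustration, assume that 10–20% of participants enter with an unresolved event and 10–25% of those worsen. That gives 0.10 × 0.10 = 1% to 0.20 × 0.25 = 5% of participants, or 2.4 to 12 of 240. A reader might take this as an estimate, and it is not one. The rates are assumed, and 240 is the maximum sample size in SAP 3.9, with enrolment at a site ending once MG0007 is active there. A participant percentage also changes only where the lost event is that person's sole event in the category.

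The conclusion assumes that a worsening is not already entered as a new, separately dated record.

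**What to change.** In SAP 8.2.1, define the analysis onset date of a worsened pre-existing event as the date its intensity first exceeded the pre-dose level after MG0004 IMP. Use that date for period assignment, most recent dose (SAP 3.6, 8.2.2 and 8.2.3) and time since infusion in the headache graphs.

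First check whether the CRF dates a change of intensity within a record; the documents do not show that it does. If it does not, state instead that a worsening is entered as a new AE record with its own start date, and say how carried-over events already in the database will be handled.

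Align Protocol 8.3.8 with 9.3.1. The SAP already follows 9.3.1, so this is a wording correction. The one-day gap at the start of the Observation Period can be closed in the same edit.

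The cost is a sentence or two in the SAP and one derived date if the CRF supports it. Otherwise it is a data-entry instruction and possibly some site queries. No new analysis is needed.

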8.2.2 Adverse events summaries

TEAEs will be summarized by the most recent dose level prior to onset of TEAEs and RLZ total, including the number and percentage of study participants and frequency. Additional details are described below:

1. Overview of TEAEs will include following categories: any TEAEs, serious TEAEs, participant discontinuation due to TEAEs, permanent withdrawal of IMP due to TEAEs,

temporary withdrawal of IMP due to TEAEs, TEAEs requiring dose change, treatment-related TEAEs, severe TEAEs, TEAEs leading to death, all deaths (AEs leading to death).

2. Incidence of TEAEs will be summarized by SOC, HLT, PT for:

- Any TEAEs
- Any TEAEs during Treatment Period
- Any TEAEs by maximum intensity (mild, moderate and severe)
- Any TEAEs by relationship
- Severe TEAEs
- Non-serious TEAEs above reporting threshold of 5% of study participants
- Fatal TEAEs
- Fatal TEAEs by relationship
- Serious TEAEs
- Serious TEAEs by relationship
- Participant discontinuation due to TEAEs
- TEAEs leading to permanent withdrawal of IMP
- TEAEs leading to temporary withdrawal of IMP
- TEAEs requiring dose change
- Treatment-emergent AESM
- Treatment-emergent AESI

3. Incidence of any TEAEs will be summarized by decreasing frequency of PT.

AESMs include severe headache, severe GI disorders (i.e., abdominal pain, diarrhea, vomiting), and opportunistic infection.

AESIs are the cases of potential Hy's Law (see [Section 8.3.1](#)).

AESMs and AESIs will be identified based on the assessment by the Investigator as recorded in the CRF. An AE will be counted as an AESM if there is a 'yes' response to the question "Adverse event of Special Monitoring?" and 'no' otherwise. An AE will be counted as an AESI if there is a 'yes' response to the question "Adverse Event of Special Interest?" and 'no' otherwise.

When applicable adverse event summaries will be ordered by alphabetical SOC, alphabetical HLT within SOC and decreasing frequency of PT in the RLZ total column for tables.

Listings of all TEAEs, all non-serious TEAEs, serious TEAEs, permanent withdrawal of IMP due to AEs, study participant discontinuation from study due to AEs, AEs leading to death, AESIs, AESMs will be presented by treatment group and participant. Persistent AEs and TEAE will be flagged in the listings. Most recent dose will be presented in listing even when the AE start date is partial.

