already started MG0004, a minimum treatment duration of 6 visits must be completed (if IMP treatment is withheld for low IgG, study participants missed dose(s) can be counted as part of the total 6 visits for completion of MG0004 and meet eligibility requirements for MG0007) and then the participant will discontinue MG0004 and have the opportunity to enter into MG0007. For study participants entering MG0007 from the treatment period of MG0004, he/she must complete the PEOT Visit in MG0004 which will serve both as the Screening Visit for MG0007 and as the EOS for MG0004. If a study participant completes the Treatment Period and is in the Observation Period of MG0004, he/she will then complete the EOS visit to serve as the Screening Visit for MG0007. Once the site is active for MG0007, no further participants will enroll in MG0004 and the study will be closed at the site once all eligible study participants have rolled over into MG0007.

An IDMC will be formed to monitor the ongoing safety of the study. The IDMC will review implications of individual and cumulative cases to continuance of the study in an ongoing fashion.

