MG0004 will then evaluate the long-term safety, tolerability, and efficacy of rozanolixizumab over a 52-week Treatment Period. An open-label study with a treatment duration of 52 weeks is considered sufficient to adequately assess long-term safety with rozanolixizumab for the proposed indication. The dose regimen for rozanolixizumab in MG0004 will be the same one that is used in MG0003 and MGC003 (equivalent to approximately [REDACTED]), although the dose may be modified based on interim analysis in MG0003 (Section 4.3). In MG0004, study participants will be rerandomized to 1 of 2 doses of rozanolixizumab, and will be allowed to switch between dose arms at the discretion of the Investigator. MG0004 will therefore allow study participants to switch their dose of study medication on an individual basis. MG0004 also offers study participants the chance to benefit from long-term treatment. MG0004

will conclude with an 8-week Observation Period, which is the anticipated duration of time required for antibodies to return to Baseline levels after rozanolixizumab treatment.

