8.3.1 Time period and frequency for collecting AE and SAE information

All SAEs will be collected from the signing of the ICF until EOS Visit at the time points specified in the Schedule of Activities (Section 1.3).

All AEs will be collected from the signing of the ICF until EOS Visit at the time points specified in the Schedule of Activities (Section 1.3).

All SAEs will be recorded and reported to the Sponsor or designee within 24 hours, as indicated in Appendix 3 (Section 10.3). The Investigator will submit any updated SAE data to the Sponsor within 24 hours of it being available.

The Investigator is specifically requested to collect and report to UCB (or its representative) any SAEs (even if the Investigator is certain that they are in no way associated with the study medication), up until the End of Study Visit for each participant, and to also inform participants of the need to inform the Investigator of any SAE within this period. Serious AEs that the Investigator thinks may be associated with the study medication must be reported to UCB regardless of the time between the event and the end of the study.

The method of recording, evaluating, and assessing causality of AE and SAE and the procedures for completing and transmitting SAE reports are provided in Appendix 3 (Section 10.3).

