If one of the doses described above is determined to be discontinued after the interim analysis in MG0003, then that dose arm will be dropped from MG0004 as well, and study participants in the affected dose arm will be transferred to the continuing dose arm. If both dose arms are used in MG0004, study participants will be allowed to switch dose arms for tolerability and efficacy reasons at the discretion of the Investigator.

In MG0004, rozanolixizumab will be administered sc on a [REDACTED] basis over a 52-week Treatment Period. At the end of the 52-week Treatment Period in MG0004, study participants will participate in an 8-week Observation Period. The maximum study duration per study participant is 60 weeks.

This open-label extension (OLE) study will be replaced by MG0007, an OLE study with [REDACTED] based on MG worsening. Upon study site approval of MG0007, as well as fulfilment of regulatory requirements, study participants will have the opportunity to rollover directly into MG0007 and will no longer have the opportunity to rollover to MG0004. In the event a study participant has already started MG0004, a minimum treatment duration of 6 visits must be completed (if IMP treatment is withheld for low IgG, study participants missed dose(s) can be counted as part of the total 6 visits for completion of MG0004 and meet eligibility requirements for MG0007) and then the participant will discontinue MG0004 and have the opportunity to enter into MG0007. For study participants entering MG0007, he/she must complete the Premature End of Treatment (PEOT) Visit in MG0004 which will serve as the Screening Visit for MG0007 or as the End of Study (EOS) Visit for MG0004. If a study participant completes the Treatment Period and still in Observation Period of MG0004, he/she will then complete EOS Visit to serve as the Screening Visit for MG0007. Once the site is active for MG0007, no further participants will enroll in MG0004 and the study will be closed at the site once all eligible study participants have rolled over into MG0007.

A schematic of the study design is provided in Figure 2-1.

Figure 2-1: Study schematic

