8.1 Extent of exposure

The following descriptive summaries will be generated using the SS by first dose received:

- a) Study IMP duration (weeks) by first dose received, calculated as follow:

$$\text{Study IMP duration (weeks)} = \frac{\text{Date of last dose} - \text{Date of first dose} + 1}{7}$$

- b) Cumulative study IMP Duration using > 0 weeks, ≥ 6 weeks, ≥ 12 weeks, ≥ 18 weeks, ≥ 24 weeks, ≥ 30 weeks, ≥ 36 weeks, ≥ 42 weeks and ≥ 48 weeks and 52 weeks;
- c) Number of Infusions Received as continuous and using the following categorical values: 1-6, 7-12, 13-18, 19-24, 25-30, 31-36, 37-42, 43-48, and 49-52.

The number of participants with dose change at each visit will be summarized using the SS by the most recent dose received.

All IMP administration details will be listed.

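### Transfer to MG0007 makes time at risk run from about 6 to 60 weeks, yet both primary safety endpoints are reported only as crude percentages and event counts

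*SAP*

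**What the plan says.** The primary objective is long-term safety and tolerability. The primary endpoints are the occurrence of TEAEs and of TEAEs leading to permanent withdrawal of study medication (Protocol 3; SAP 2.2.1.1). Protocol 4.2 rests the adequacy of the design on duration: "An open-label study with a treatment duration of 52 weeks is considered sufficient to adequately assess long-term safety with rozanolixizumab". The estimand text in Protocol 3 gives the aim as comparing the safety of two dose levels over long-term treatment.

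Protocol 4.1 also provides for early exit. Once MG0007 is available, for someone already in MG0004 "a minimum treatment duration of 6 visits must be completed", and "then the participant will discontinue MG0004 and have the opportunity to enter into MG0007". Doses missed for low IgG may count towards the 6 visits. For transfers from the Treatment Period, the premature end-of-treatment (PEOT) visit is one "which will serve both as the Screening Visit for MG0007 and as the EOS for MG0004". SAP 2.3 carries the same 6-visit minimum. Protocol 8.3.1 sets the collection window: "All AEs will be collected from the signing of the ICF until EOS Visit".

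SAP 8.2.1 and 8.2.2 present TEAEs by most recent dose before onset and for the rozanolixizumab total, "including the number and percentage of study participants and frequency". For IMP duration and number of infusions, SAP 8.1 says: "The following descriptive summaries will be generated using the SS by first dose received". SAP 5.1 adds participant counts by visit and lists transition to MG0007 as a discontinuation reason.

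**The concern.** A crude percentage puts everyone treated in the denominator, however long each was observed. Here observation length depends partly on when a site opened MG0007, which is unrelated to the drug. A participant who leaves after about 6 weeks counts the same as one followed for 60, and an event that would have occurred in MG0004 after transfer is not recorded there.

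Two readings are at stake. First, a reader will take the percentage as the long-term incidence that the primary objective asks for. Secondly, the dose columns will be compared, because that is the protocol's stated aim. Under a most-recent-dose grouping, each column's time at risk depends on switching as well as on transfer, and no planned table shows how much time stands behind each column. Late-onset events are the most exposed to this. So is the second primary endpoint, to the extent that withdrawals build up over the year.

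**Working it through.** **Inputs from the documents.** Treatment Period 52 weeks, Observation Period 8 weeks, maximum 52 + 8 = 60 weeks, as stated (Protocol 4.4; SAP 3.2.2). Minimum before transfer: 6 visits, about 6 weeks on the weekly schedule. Maximum N = 240 (SAP 3.9), used only in a simulation. The plan states no expected event rate, power or precision to reproduce.

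**Assumptions.** The documents do not give the true 52-week incidence p, the share transferring s, the transfer week t or the timing of events. All values below are illustrative.

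**Step 1: constant hazard.** Let h = −ln(1 − p)/52. With t uniform on 6 to 52 weeks, the expected crude proportion among transfers is 1 − [exp(−6h) − exp(−52h)]/(46h).

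For p = 10%, h = 0.002026. Then exp(−6h) = 0.9879, exp(−52h) = 0.9000 and 46h = 0.0932, so the result is 1 − 0.0879/0.0932 = 5.7%. With half transferring, 0.5 × 10% + 0.5 × 5.7% = 7.8%.

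| True 52-week incidence | s = 25% | s = 50% | s = 75% | s = 100% |
|---|---|---|---|---|
| 5% | 4.5% | 3.9% | 3.4% | 2.8% |
| 10% | 8.9% | 7.8% | 6.8% | 5.7% |
| 80% | 73.9% | 67.9% | 61.8% | 55.7% |

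If half transfer and all of them leave at week 6, a true 10% reads 0.5 × 10% + 0.5 × (1 − 0.9^(6/52)) = 5.6%.

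**Step 2: front-loaded events.** Suppose 80% of the 52-week cases occur by week 6, the rest are spread evenly over weeks 6 to 52, and half transfer uniformly. Then 10% reads 0.5 × 10% + 0.5 × 10% × (0.8 + 0.2 × 0.5) = 9.5%. By the same formula 80% reads 76.0%. If every first event occurs by week 6, there is no shortfall. The crude figure cannot exceed the full-follow-up figure, so the error is downward or zero.

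**Step 3: would time-adjusted measures help?** Under constant hazard, a simulation (N = 240, p = 10%, half transferring, 4,000 runs) gave a crude 7.8%, a Kaplan-Meier estimate of 10.0% at 52 weeks, and 0.106 first events per 52 person-weeks against a true 0.105.

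In the front-loaded case a single rate does worse. Take early cases as averaging 3 weeks to onset.
- Full follow-up: person-time is 0.90 × 52 + 0.08 × 3 + 0.02 × 29 = 47.62 weeks per participant. The rate is 0.10/47.62 × 52 = 0.109.
- Transfers: person-time is 0.90 × 29 + 0.08 × 3 + 0.02 × 21.33 = 26.77 weeks, with 0.09 events.
- Half transferring: 0.095 events over (47.62 + 26.77)/2 = 37.19 weeks gives 0.133. That is 0.133/0.109 = 1.22, about 22% high, while the crude percentage is 5% low in relative terms.

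A participant-year rate alone is therefore not enough; an estimate at fixed weeks is needed beside it.

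**Step 4: can exposure already planned serve as the denominator?** For the rozanolixizumab total, yes, approximately: the two first-dose groups add up to total IMP duration whatever the switching. For the dose columns, no: a switcher's whole duration sits under the first dose, while the TEAE is assigned to the most recent dose.

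**The case against.** The best defence is that the plan does what its endpoints say. They are worded as occurrence, and number, percentage and event count summarise occurrence directly. Neither document names 52-week incidence as the target. Unequal duration was also considered: Protocol 3 mentions differing treatment lengths and argues that a hypothetical estimand accounting for them would lean too heavily on assumptions. The counts by visit, the IMP-duration bands and the MG0007 disposition reason show readers that follow-up was cut short. Finally, events may cluster early, in which case little is lost and a participant-year rate could mislead more than the crude figure.

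Much of this stands. The crude tables are right for the endpoint wording and should stay. The size of any shortfall is unknown and may be nil. A rate on its own would not be a sound remedy, as Step 3 shows.

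It does not close the gap. The objective is long-term safety, and 52 weeks is the stated ground for adequacy. The protocol's argument against a hypothetical estimand does not apply to a descriptive rate or to a curve censored at transfer. Transfer to MG0007 is not among the main intercurrent events it lists, so the treatment-policy choice does not settle how to handle it. The disclosure tables show that follow-up varied, but they give no time at risk for the dose columns and none to first event.

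**Conclusion.** The point holds in a conditional form. Time at risk in MG0004 varies from about 6 to 60 weeks for administrative reasons, and no planned summary of either primary endpoint takes account of it. As 52-week incidence, the crude percentage is too low or, at best, unchanged. In the illustration with half transferring uniformly, a true 10% reads between 7.8% (constant hazard) and 9.5% (80% of cases by week 6). These values rest on assumed transfer and event timing, and on transfer being unrelated to a participant's risk.

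A reader might infer more than the documents support:
- That the percentages will be far too low. This needs nearly everyone to leave early and events to keep accruing through the year; the documents establish neither.
- That the exposure table is no use as a denominator. It fails for the dose columns only.
- That every transfer loses the 8-week observation. Participants already in the Observation Period complete the EOS visit before moving (Protocol 4.1).
- That results cannot be set against MG0003 or MG0007. Those plans are not available here, and the SAP's amendment log says the adverse event summaries were aligned with MG0003.

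The change should be made, but its absence does not invalidate the planned tables.

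**What to change.** Keep the crude tables and make these additions.

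- **SAP 8.2.2, rates.** For any TEAE, TEAEs leading to permanent IMP withdrawal, serious TEAEs, severe TEAEs and adverse events of special monitoring, give exposure-adjusted incidence rates (participants with a first event) and event rates, each per 100 participant-years. Start time at risk at the first MG0004 dose. End it at the earliest of first event (incidence rates only), close of the TEAE window, and EOS, PEOT-as-EOS or last contact. State that first event is counted within each dose column for dose-specific rates and once overall for the rozanolixizumab total.
- **SAP 8.2.2, estimates at fixed weeks.** For the two primary endpoints, add Kaplan-Meier or cumulative-incidence estimates by first dose received and for the rozanolixizumab total, censored at transfer or last contact. First dose is fixed at entry and is the classification that Protocol 3 uses for safety.
- **SAP 8.1.** Add participant-years by most recent dose, with a switcher's time split at the switch date, and for the rozanolixizumab total.

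The cost is a few more outputs from dose, onset and visit dates already collected, with no change to conduct. The results may look less favourable than the crude percentages. Participant-year rates assume a roughly constant hazard and can read high when events come early, so the fixed-week estimates should be shown with them.
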